9.6.1 Economic analysis

Economic analysis will focus on determining the differences in the patient pathways between the three groups in terms of their costs and benefits. Analysis will therefore take a number of different forms.

Incremental Cost Effectiveness Ratios (ICER) will be calculated against the base case:

A. Inhaled fluticasone propionate 100micrograms twice daily plus placebo tablet once daily .

The other two scenarios:

B. Inhaled fluticasone propionate 100micrograms and salmeterol 50micrograms twice daily (combination inhaler) plus placebo tablet once daily

C. Inhaled fluticasone propionate 100micrograms twice daily plus montelukast 5mg tablet once daily will be compared against the base case.

ICERs calculate the ratio of the difference in cost to the difference in outcome between the two groups. In terms of outcome, the ICER will be based on the difference in the number of exacerbations between the groups. Further ICERs based on quality of life could also be calculated.

Cost effectiveness acceptability curves (CEACs) will be calculated for each of the three regimes showing the probability that each option is cost effective at different willingness to pay thresholds.

A subsidiary economic analysis may evaluate the cost of exacerbations in terms of the average cost per exacerbation and then cost the treatment alternatives in terms of exacerbations averted. This subsidiary analysis is a useful supplement to the main analysis. Cases averted are a useful tool for presentation of the data.

10 PHARMACOVIGILANCE

10.1 Terms and Definitions

The Medicines for Human Use (Clinical Trials) Regulations 2004 (SI 2004/1031) definitions:

Adverse Event (AE)

Any untoward medical occurrence in a subject to whom a medicinal product has been administered, including occurrences which are not necessarily caused by or related to that product.

Adverse Reaction (AR)

Any untoward and unintended response in a subject to an investigational medicinal product which is related to any dose administered to that subject.

Unexpected Adverse Reaction (UAR)

An adverse reaction the nature and severity of which is not consistent with the information about the medicinal product in question set out in:

In the case of a product with a marketing authorization, in the summary of product characteristics for that product

In the case of any other investigational medicinal product, in the investigator's brochure relating to the trial in question.

Serious Adverse Event (SAE), Serious Adverse Reaction (SAR) or Suspected Unexpected Serious Adverse Reaction (SUSAR)

Any adverse event, adverse reaction or unexpected adverse reaction, respectively, that:

- results in death
- is life-threatening* (subject at immediate risk of death)
- requires in-patient hospitalisation or prolongation of existing hospitalisation**
- results in persistent or significant disability or incapacity, or
- consists of a congenital anomaly or birth defect
- Other important medical events

*'life-threatening' in the definition of 'serious' refers to an event in which the patient was at risk of death at the time of the event; it does not refer to an event which hypothetically might have caused death if it were more severe.

**Hospitalisation is defined as an inpatient admission, regardless of length of stay, even if the hospitalisation is a precautionary measure for continued observation. Hospitalisations for a pre-existing condition, including elective procedures that have not worsened, do not constitute an SAE.

***Other important medical events that may not result in death, be life-threatening, or require hospitalisation may be considered a serious adverse event/experience when, based upon appropriate medical judgment, they may jeopardise the subject and may require medical or surgical intervention to prevent one of the outcomes listed in this definition

10.2 Notes on Adverse Event Inclusions and Exclusions

10.2.1 Include

- An exacerbation of a pre-existing illness
- An increase in frequency or intensity of a pre-existing episodic event/condition
- A condition (even though it may have been present prior to the start of the trial) detected after trial drug administration
- Continuous persistent disease or symptoms present at baseline that worsens following the administration of the study/trial treatment

10.2.2 Do Not Include

- Medical or surgical procedures - the condition which leads to the procedure is the adverse event

- Pre-existing disease or conditions present before treatment that do not worsen
- Situations where an untoward medical occurrence has occurred e.g. cosmetic elective surgery
- Overdose of medication without signs or symptoms
- The disease being treated or associated symptoms/signs unless more severe than expected for the patient's condition

10.2.3 Reporting of Pregnancy

Study participants will not routinely be tested for pregnancy as part of the trial screening process. Any pregnancy which does occur during the course of the study should be reported to the MCRN CTU immediately. The investigator should discuss the risks of continuing with the pregnancy with the patient and the possible effects on the foetus if they continue on trial treatment. It is at the investigator's discretion to decide whether the individual should be instructed to stop taking study drugs. All pregnancies that occur during trial treatment, or within seven days of finishing treatment, need to be followed up until completion and reported separately.

10.3 Notes Severity / Grading of Adverse Events

The assignment of the severity/grading should be made by the investigator responsible for the care of the participant using the definitions below.

Regardless of the classification of an AE as serious or not, its severity must be assessed according to medical criteria alone using the following categories:

Mild: does not interfere with routine activities

Moderate: interferes with routine activities

Severe: impossible to perform routine activities

A distinction is drawn between serious and severe AEs. Severity is a measure of intensity (see above) whereas seriousness is defined using the criteria in section 10.1, hence, a severe AE need not necessarily be a Serious Adverse Event.

10.4 Relationship to Trial Treatment

The assignment of the causality should be made by the investigator responsible for the care of the participant using the definitions in Table 3.

If any doubt about the causality exists the local investigator should inform the study coordinating centre who will notify the Chief Investigator. In the case of discrepant views on causality between the investigator and others, the MHRA will be informed of both points of view.

Table 3: Definitions of Causality

Relationship	Description
Unrelated	There is no evidence of any causal relationship. N.B. An alternative cause for the AE should be given
Unlikely	There is little evidence to suggest there is a causal relationship (e.g. the event did not occur within a reasonable time after administration of the trial medication). There is another reasonable explanation for the event (e.g. the participant's clinical condition, other concomitant treatment).
Possibly	There is some evidence to suggest a causal relationship (e.g. because the event occurs within a reasonable time after administration of the trial medication). However, the influence of other factors may have contributed to the event (e.g. the participant's clinical condition, other concomitant treatments).
Probably	There is evidence to suggest a causal relationship and the influence of other factors is unlikely.
Almost certainly	There is clear evidence to suggest a causal relationship and other possible contributing factors can be ruled out.

10.5 Expectedness

An AE whose causal relationship to the study drug is assessed by the investigator as “possible”, “probable”, or “almost certainly” is an Adverse Drug Reaction.

All events judged by the investigator to be possibly, probably, or almost certainly related to the IMP, graded as serious and **unexpected** (see section 10.2 and SPCs for list of Expected Adverse Events) should be reported as a SUSAR.

10.6 Follow-up After Adverse Events

All adverse events should be followed until satisfactory resolution or until the investigator responsible for the care of the participant deems the event to be chronic or the patient to be stable.

When reporting SAEs and SUSARs the investigator responsible for the care of the participant should apply the following criteria to provide information relating to event outcomes: resolved; resolved with sequelae (specifying with additional narrative); not resolved/ongoing; ongoing at final follow-up; fatal or unknown.

10.7 Reporting Procedures

All adverse events should be reported. Depending on the nature of the event the reporting procedures below should be followed. All adverse events will be reported and recorded from the point that the participant provides informed consent and throughout the trial treatment period up until seven days after the patient has taken the final dose of investigational medicinal product. Any questions concerning adverse event reporting should be directed to the MCRN CTU in the first instance. A flowchart is given below to aid in determining reporting requirements.

[figure not shown]

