Those who are clinically worse may be withdrawn from randomised treatment and given alternative treatment according to clinician's advice as in routine practice. The decision to withdraw the patient from trial treatment is based on the patient's current clinical presentation and the review of information on symptoms/exacerbations etc collected in the hand held record over the preceding weeks. The decision is made at the discretion of the investigator using their informed clinical opinion. The reason for discontinuation of trial treatment must be documented on the CRF. Follow-up should be continued until the end of the trial as per the study visit schedule.

In certain circumstances, the PI/RN may conduct the T+24 study visit at the family home where it is appropriate and necessary to do so. The PI/RN must only conduct a study visit in the family home if this has been authorised for their site by the coordinating centre and appropriate lone working procedures are in place.

Randomisation + 36 weeks (Telephone call)

Symptoms, exacerbations and beta₂ agonist use will be ascertained from the patient and/or their carer/s. The RN will check that they are continuing to complete the hand held record and that they have completed the inserted Health Economics questionnaire for the time period since their last clinic visit. They will be asked to remove the completed questionnaire and place it to the back of the record to avoid any confusion. The RN will remind them to begin a new Health Economics questionnaire to be used until their next appointment.

Adverse events will be reported and recorded. Those who have achieved control of their asthma symptoms will continue on the trial treatment. For those whose symptoms have not improved but are no worse, the RN will discuss their willingness to continue with randomised treatment. Those whose asthma symptoms appear to be worse will either be offered an unscheduled study appointment with a member of the research team (if possible) or advised to visit their General Practitioner to seek further medical advice. If the practitioner believes they are clinically worse the patient may be withdrawn from randomised treatment and given alternative treatment according to clinician's advice as in routine practice. The reason for discontinuation of trial treatment must be documented on the CRF. Follow-up should be continued until the end of the trial as per the study visit schedule.

Randomisation + 48 weeks (Clinic visit)

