Symptoms, exacerbations and beta₂ agonist use will be ascertained by reviewing the hand held record with the patient and their carer/s. The two Health Economics questionnaires completed throughout the time period since the last clinic visit will be checked for completeness and removed. Final Quality of Life assessments will be administered (interviewer [if child is 10 years of age or younger], patient [if aged 11 years or more] and carer administered) and a basic physical examination will be performed, including height and weight measurements. Further examination will be symptom led. Spirometry will be carried out to measure the patient's FEV₁, FVC and FEV₁/FVC ratio (best of three before and after bronchodilator). Adverse events will be reported and recorded.

Patients will be asked to provide current details for their General Practitioner (GP). They will be informed that their GP will be provided with details of which treatment they have been taking within seven days. If the patient was under the care of a different clinician for their asthma management prior to entering the study, that clinician will also be provided with details of the treatment wherever possible. The PI/RN will discuss future management with patients and their carer/s.

Table 2. Schedule of Study Procedures

Procedures	Screening (T-4)	Baseline (T0 [clinic])*	Follow-Up Schedule (weeks)				Premature Discontinuation
			T+ 8 Weeks (clinic)	T+ 24 Weeks (clinic)	T+ 36 Weeks (telephone)	T+ 48 Weeks (clinic) Study Completion	
Signed Consent Form	X						
Assessment of Eligibility Criteria	X	X					
Quality of Life Questionnaires Administered		X	X	X		X	X
Health Economics Questionnaire Completed			X	X	X	X	X
FEV ₁ , FVC, FEV ₁ /FVC Ratio		X				X	(X)
Review Patient Held Record	X	X	X	X	X	X	X
Review of Medical History	X	X					
Review of Concomitant Medications	X	X	X	X	X	X	X
Study Intervention		X	X	X	X		
Physical Exam	Complete	X					X
	Symptom-Directed		(X)	(X)	(X)	(X)	
	Vital Signs		X	(X)	(X)	(X)	(X)
Assessment of Adverse Events		X	X	X	X	X	X
Special Assay or Procedure		X					

(X) – As indicated/appropriate.

*At baseline, all procedures should be done before study intervention.

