8.3 Procedures for Assessing Safety

An assessment of adverse events will be undertaken at each study visit from baseline (T0) to study completion (T+48). These reviews will be carried out by the PI or RN conducting the visit or telephone call.

Adverse event reporting is detailed fully in Section 10 (Pharmacovigilance).

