9.6 Analysis Plan

The study will be analysed and reported using the 'Consolidated Standard of Reporting Trials' ('CONSORT')^{15,16} and the ICH E9 guidelines.

A full and detailed statistical analysis plan will be written prior to the conduct of the final analysis according to the MCRN CTU Statistical Analysis Plan SOP. To provide a pragmatic comparison of the policies of the different treatments, primary analyses will be performed on an intention to treat basis, analysing all patients according to the treatment group originally allocated. A sensitivity analysis using the per protocol or complier average causal effect (CACE) population as appropriate will be explored to demonstrate robustness of the results. For the overall safety and tolerability assessment, the set of patients to be summarised will be defined as those subjects who received at least one dose of the study drug.

Missing data will be handled by considering the robustness of the complete case analysis to sensitivity analyses using different imputation assumptions informed by data collected on reasons for missing data. Data relating to the primary outcome (oral steroid usage) for those patients who fail to attend for the 48 week assessment visit can be obtained from their GP.

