Time to first exacerbation requiring treatment with a short course of oral corticosteroids will be calculated for each child and compared across treatment groups using Kaplan-Meier curves and log-rank test with relative effects of treatments summarised using hazard ratios and 95% confidence intervals. The seasonality of having an asthma exacerbation episode will be explored by fitting season as a time-dependent covariate in the model for time to first exacerbation.

Time to withdrawal of randomized treatment will be calculated for each child and compared across treatment groups using Kaplan-Meier curves and log-rank test with relative effects of treatments summarised using hazard ratios and 95% confidence intervals. To examine different reasons for treatment withdrawal (competing risks of unacceptable adverse effects and inadequate asthma control) a cumulative incidence analysis will be undertaken. This approach does not assume competing risks are independent and allows the assessment of cause-specific withdrawal in the presence of other competing risks. All adverse events will be categorised appropriately and the number of patients with occurrences of each event summarised according to treatment group supplemented by calculation of confidence intervals wherever this aids interpretation.

The percentage of school days missed (transformed if appropriate) will be analysed and compared between treatment groups using analysis of variance. The number of hospital admissions will be summarised and compared between treatment groups using bootstrapping techniques which allow comparisons between groups to be based upon the mean difference while making allowance for the non-normal distribution in the calculation of confidence intervals and p-values (Metcalf et al 2003¹⁷). Lung function at 48 weeks will be compared between treatment groups using analysis of covariance (adjusted by baseline lung function). Number of doses of rescue beta₂ agonist therapy prescribed over 48 weeks (transformed if appropriate) will be analysed and compared between treatment groups using analysis of variance. Blinded distribution data will be reviewed and the statistical analysis plan amended accordingly.

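### Section 10.7 closes adverse event recording seven days after the last dose, while 8.1, 8.3, Table 2 and 10.8 continue it to T+48, so AE collection for children who stop treatment early is contradictory and could become uneven between arms

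*Protocol*

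**What the plan says.** **Protocol 10.7** sets the window for AE reporting. It opens "from the point that the participant provides informed consent", which is the T-4 visit, and runs "throughout the trial treatment period up until seven days after the patient has taken the final dose of investigational medicinal product".

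**Protocol 8.3** sets a different one: "An assessment of adverse events will be undertaken at each study visit from baseline (T0) to study completion (T+48"). It makes no exception for children off treatment, and it refers to Section 10 for the detail of reporting. In **Table 2**, the row "Assessment of Adverse Events" has six marks, which read as T0, T+8, T+24, T+36, T+48 and premature discontinuation, with none at screening. The descriptions of the T+8, T+24, T+36 and T+48 contacts in **8.1** each say that AEs are reported and recorded.

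**Protocol 8.1** keeps children who are withdrawn from randomised treatment on the same schedule: "Follow-up should be continued until the end of the trial as per the study visit schedule". Sections 5.3 and 5.3.2 likewise ask them to allow further data collection.

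**Protocol 10.8** makes the investigator responsible for every AE seen or notified in the course of the study, whether or not it is related to treatment.

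**Protocol 9.6** reports AEs as "the number of patients with occurrences of each event summarised according to treatment group". AEs are a secondary endpoint (4.2, 9.3.2). So is time to treatment withdrawal for lack of efficacy or side effects, which 9.6 compares across arms.

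**The concern.** A child who stops treatment early but stays in follow-up falls under two rules. Section 10.7 says recording has ended; 8.1, 8.3, Table 2 and 10.8 say it continues. One site can stop recording a week after the last dose while another records to T+48, and each can point to the protocol.

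This bears on the comparison of arms because the planned summary counts patients with an event. Under 10.7, a child's chance of being counted depends on how long the child stays on treatment. Treatment withdrawal is itself an outcome that could differ by arm. If it does, the arm with more withdrawals has less time in which events can be recorded and could look safer than it is.

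The SAP can choose an analysis window, but it cannot recover events that a site was told not to record. The collection rule therefore has to be settled in the protocol.

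**Working it through.** The protocol states no figure on this point, so there is none to reproduce. The check has two parts.

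**1. How far the rules differ.** Inputs: contacts at T+8, T+24, T+36 and T+48 (8.1); treatment for at most 48 weeks (7.3.1); one week after the last dose (10.7).

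Post-randomisation weeks recorded under 10.7 = weeks on treatment + 1. Under 8.3 and Table 2 the figure is 48.

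| Last dose | 10.7 window | 8.3 / Table 2 window | Weeks in dispute |
|---|---|---|---|
| T+8 | 8 + 1 = 9 | 48 | 48 − 9 = 39 |
| T+24 | 24 + 1 = 25 | 48 | 48 − 25 = 23 |
| T+36 | 36 + 1 = 37 | 48 | 48 − 37 = 11 |
| T+48 | 48 + 1 = 49 | 48 | none lost; 10.7 runs one week longer |

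At the start, 10.7 opens at T-4 and 8.3 and Table 2 at T0. The difference is the run-in of about four weeks (24 to 30 days in 8.1).

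**2. What this could do to the comparison by arm.** The protocol gives neither AE risks nor withdrawal rates, so everything here is assumed. Suppose there is no true difference between arms, a constant hazard, a 48-week event risk p, and early stoppers who all stop at T+8.

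- Hazard per week: h = −ln(1 − p)/48.
- Chance of a recorded event in w weeks: g(w) = 1 − exp(−h·w).
- Proportion with an event in an arm where a fraction d stops at T+8, under 10.7: d·g(9) + (1 − d)·g(49).

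For p = 20%: h = 0.2231/48 = 0.00465, g(9) = 0.041 and g(49) = 0.204.

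- Arm with 10% stopping: 0.1 × 0.041 + 0.9 × 0.204 = 0.187.
- Arm with 20% stopping: 0.2 × 0.041 + 0.8 × 0.204 = 0.171.
- Apparent risk ratio, from unrounded values: 0.913.

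Over a range of assumptions:

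| 48-week risk | 10% v 20% stop at T+8 | 10% v 30% stop at T+8 |
|---|---|---|
| 5% | 0.912 | 0.823 |
| 20% | 0.913 | 0.826 |
| 50% | 0.918 | 0.836 |

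Later stopping shrinks the effect. For p = 20% and stopping at T+24, g(25) = 0.110. The arms then show 0.1 × 0.110 + 0.9 × 0.204 = 0.194 and 0.2 × 0.110 + 0.8 × 0.204 = 0.185, a ratio of about 0.95. With equal withdrawal in both arms the ratio is 1. With recording to T+48 for every child, no such distortion arises.

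**The case against.** The best defence is that the passages do different jobs: 8.3 says when families are asked, and Section 10, to which 8.3 refers, says what is reportable. A cut-off seven days after the last dose is also a sound on-treatment window, because withdrawn children may have moved to other treatment. The reporting flowchart in 10.7 is not visible to us and might clarify the rule. These points have some force, but they do not remove the conflict. The 8.1 visit text says AEs are recorded at those contacts, not merely asked about, and 10.8, inside Section 10 itself, has no on-treatment limit. An on-treatment window can be applied at analysis to data collected to T+48; the reverse is not possible.

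It is also fair to say that the effect needs early withdrawal that differs by arm. That stands, and it limits the conclusion.

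Three stronger readings may tempt a reader, and the protocol does not support them:

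- *Run-in events dilute the comparison by arm.* Recording from consent is an ordinary collection rule. Section 9.6 does not say that run-in events enter the tables by arm, and that choice is commonly left to the SAP. Events before allocation are balanced in expectation: if counted, they would pull ratios towards 1 but favour no arm.
- *The safety set takes in children who had only the run-in inhaler.* It is "defined as those subjects who received at least one dose of the study drug". Reading the open-label inhaler as the study drug is strained: it would also admit registered children who were never randomised and have no arm, and Table 2 marks study intervention only from T0.
- *Serious events after stopping treatment are lost.* Section 10.8 covers AEs throughout the study, 10.9 recommends expedited reporting of post-study SUSARs, and hospital admissions are a separate secondary outcome. These routes mitigate the problem in part. They do not secure the recording of non-serious events, or of every serious event, at a site that follows 10.7.

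**Conclusion.** The contradiction is real and lies in current text. Sections 10.7, 8.1, 8.3, Table 2 and 10.8 disagree on when AE recording ends for a child who stops treatment but stays in follow-up, by 39 weeks for stopping at T+8 and 23 weeks for T+24. Section 10.7 also disagrees with 8.3 and Table 2 on when it starts.

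The consequence for the comparison by arm is a risk, not an established bias. It depends on enough children stopping early, on withdrawal differing between arms, and on sites following 10.7. Under the assumed 10% versus 20% stopping at T+8, constant hazard and no true difference, the arm with more withdrawals shows a risk ratio of about 0.91, and about 0.82 to 0.84 with 10% versus 30%. The protocol gives no rates by which to say how likely this is. The correction is still worth making, because it is cheap and the data cannot be recovered later.

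**What to change.** Reconcile 10.7 with 8.1, 8.3, Table 2 and 10.8 as a single collection rule. Record AEs from consent. For every randomised child still in follow-up, on or off treatment, continue to T+48, or to seven days after the last dose if that is later. Word 8.3 and Table 2 so that the T0 review covers events since consent.

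Collect the onset date of every AE and the date of the last dose. On-treatment counts (to seven days after the last dose) and all-follow-up counts from randomisation can then both be shown by arm.

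The visits and the telephone contact already take place, so the cost is wording and some extra AE forms for children who have stopped treatment.
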